- H1 Metabolic phenotypes based on basic mechanisms of adipose tissue are associated to the cardiovascular risk modification after bariatric surgery.
- H0. Metabolic phenotypes based on basic mechanisms of adipose tissue are NOT associated to the cardiovascular risk modification after bariatric surgery.

GENERAL OBJETIVE

To evaluate the association of the cardiovascular benefit of the obese patient after bariatric surgery with the basic mechanisms of adipose tissue (metabolic profile)

SPECIFIC OBJECTIVES

- Characterize the basal (pre-surgical) metabolic profile of adipose tissue.
- Evaluate post-surgical modification of cardiovascular prognosis
- Determine the association of the cardiovascular prognosis modification (risk subgroups) with the basal metabolic profile.

DESIGN

This is an OBSERVATIONAL study, of a prospective cohort follow-up. We will study morbidly obese patients who undergo bariatric surgery (this is not a proposal of the present protocol, it is routinely done as a treatment for morbid obesity in the CMN "20 de Noviembre", ISSSTE, and it would also be carried out although the patient does not participate in this study). It was considered that the independent variable is the change in cardiovascular risk after bariatric surgery and the dependent variable is the basal metabolic profile of adipose tissue. This order of variables was decided by methodological strategy, since it will be more convenient to determine and stratify based on the change in cardiovascular risk, than based on the basal metabolic profile of adipose tissue.

$$n = \frac{(Z^{\alpha/2})^2 (p(1-p))}{d^2}$$

where:

n = sample size.

$Z^{\alpha/2} = Z$

value of the alpha error with a confidence of 95%, assigning alpha = 0.05

p =

Expected population prevalence for the event under study (according to previous reports).

d

=difference between the expected population prevalence value and the acceptable error. Considering the average difference in the modification of the basic mechanisms in adipose tissue associated with metabolic risk in similar studies

$$\begin{array}{ll}
 (1.96)^2 (0.20 (1-0.20)) & 0.614 \\
 n = \frac{\text{_____}}{(0.13)^2} & n = \frac{\text{_____}}{0.0169} = 36.3
 \end{array}$$

Additionally, for reasons of comparison and standardization of results, a C group would be considered: 10 non-obese patients undergoing non-bariatric surgery.

Definition of the observation units.

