Patients with morbid obesity subjected to bariatric surgery, with significant modification of cardiovascular risk in the postoperative period.

Definition of the control group

Due to the observational design of the before-after evaluation (of bariatric surgery), the morbidly obese patient in the pre-surgical baseline is his own reference ("control") for the postoperative period. It is also considered non-obese subjects subjected to abdominal surgery eg. Hernioplasty, fundoplication etc. to know the "normal" metabolic profile of adipose tissue.

Inclusion criteria

- Men and women.
- Over 18 years.
- With morbid obesity and candidates for bariatric surgery, under the routine of the treating service.
- Signature of acceptance of your participation, through informed consent.

Exclusion criteria.

- Medication with potential effect on fatty tissue or cardiovascular risk in the last month.
- Serious infections in the last month.
- Clinically unstable conditions.

Elimination criteria.

- Desire not to continue in the study
- Samples or insufficient information for an adequate analysis.

Definition of variables and units of measurement.

Definition of variables and units of measurement.			
Variable	Dependent / Independent	Type	Units of measurement
Total body fat, visceral and subcutaneous	Dependent	Discontinuous Quantitative	Percentage
Serum markers of inflammation PCR and IL-6	Dependent	Quantitative continuous	µUI / dL
Serum adipokines: leptin and adiponectin	Dependent	Quantitative continuous	µUI / dL
Differentiation and hypertrophy of adipocytes and angiogenesis	Dependent	Qualitative dichotomous	Present or absent
Pro-inflammatory markers at tissue level	Dependent	Qualitative dichotomous	Present or absent
Oxidative stress and tissue endoplasmic reticulum	Dependent	Qualitative dichotomous	Present or absent
Insulin sensitivity	Dependent	Qualitative dichotomous	Sensitive or not sensitive
HOMA	Dependent	Qualitative dichotomous	Higher or lower than 15
Prognostic scales mortality due to independent cardiovascular cause	Independent	Quantitative discontinuous	Own rating
Flow mediated dilatation	Independent	Quantitative discontinuous	Percentage
Carotid intima media thickness	Independent	Quantitative discontinuous	Millimeters

Selection of sources, methods, techniques and procedures for collecting information

With the acceptance of the Institutional Ethics, Research and Biosafety Committees, patients will be invited and included according to the selection criteria.

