To study the characteristics of each metabolic profile, the following variables will be analyzed:

- a) Adipose tissue (visceral and subcutaneous) where the degree of differentiation and hypertrophy of adipocytes and angiogenesis will be determined by morphometric methods of histopathology; as well as markers of inflammation, oxidative stress, endoplasmic reticulum stress and adipose tissue dysfunction through immunohistochemistry and in vitro tests on isolated adipocytes.
- b) Liver tissue the degree of steatosis, steatohepatitis and fibrogenesis, considered as clinical progression of metabolic damage, will be determined.
- c) Serum level, inflammation markers (TNFa, CRP and IL-6) and adipokines (leptin, adiponectin, resistin) will be determined by ELISA.

Finally, in all groups, follow-up variables related to post-surgical modification of cardiovascular risk will be determined; through:

Prognostic scales of cardiovascular mortality: They will be determined by Drs. [name] and [name], based on probability calculation with variables such as age, gender, co-morbidities, etc. using Framingham or SCORE scales. Place: Clinical Research Division, CMN "November 20", ISSSTE.

Determination of serum markers of endothelial dysfunction and ankle / arm index. They will be determined by [name] [name] and associated researchers, using commercially available ELISA kits and direct determination of systolic pressure in the ankle and arm, with the help of Doppler scan type Doptone, respectively. Place: Biomedical Research Laboratory and Clinical Research Division, CMN "November 20", ISSSTE.

Determination of subclinical atherogenesis (thickness of the carotid intima media). It will be determined by the Department of Imaging, with the support of [name]. The Doppler transducer will be placed in the neck and the common carotid artery will be located, then the thickness of the intimal vascular mean will be determined 1 cm from the carotid bifurcation. The determination will be made by two observers to estimate the inter-observer correlation. Place: Department of Imaging, CMN "November 20", ISSSTE.

The determination of these variables of cardiovascular risk modification will be determined basally and periodically at 3, 6 and 9 months after bariatric surgery, in all groups.

Definition of the processing plan and presentation of the information

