Data analysis will be done through descriptive statistics applied to demographic variables, and inferential statistics, which will include difference of averages, correlation, strength of association and relative risk, as well as multivariate logistic regression analysis to evaluate independent associations. With the variables most associated with the modification of cardiovascular risk, a metabolic profile will be established as a predictive model of the greatest cardiovascular benefit after bariatric surgery. Statistical significance will be considered with $p < 0.05$

ETHICAL CONSIDERATIONS

This study is considered as minimal risk. Bariatric surgery (this procedure is not a proposal of the present protocol, it is routinely done as a treatment for morbid obesity in the CMN "20 de Noviembre", ISSSTE and would also be done if the patient does not participate in the study) will be performed according to the routine procedures of the Department of Bariatric Surgery. The project complies with the guidelines and recommendation of the Declaration of Helsinki. The protocol will be submitted to the Ethics and Institutional Research Committee. All patients will be asked to read and sign informed consent.

BIOSECURITY CONSIDERATIONS.

Bariatric surgery procedures are not part of this investigation. In any case, it is emphasized that this project does not alter the surgical procedure and routine biosecurity measures, which are based on the best clinical practice and international recommendations (Neff KJ, le Roux CW, Bariatric surgery: a best practice article. *Pathol* 2013; 66: 90-8). Sampling during surgery will be done in accordance with the Regulation of the General Health Law on Health Research, respecting aspects of taking the appropriate measures to avoid any risk or damage to research subjects (includes adequate preoperative assessment). , biosecurity measures typical of an operating room and sampling by an experienced surgeon). In any case, the privacy of the individual subject of the investigation will be protected, and it will be sought to limit the likelihood that the subject will suffer any harm as a result of the study.

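### The elimination criteria drop enrolled patients who stop or have undefined insufficient information, and no planned method uses their earlier data, so the analysis becomes one of retained patients only

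*Combined protocol and SAP*

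**What the plan says.** The protocol lists elimination criteria separately from the inclusion and exclusion criteria. There are two: "Desire not to continue in the study" and "Samples or insufficient information for an adequate analysis". The first can arise only after enrolment, and in practice so does the second. Neither is tied to a visit, a variable or an amount of missing data.

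Adipose tissue is taken during surgery. The cardiovascular risk measures "will be determined basally and periodically at 3, 6 and 9 months after bariatric surgery, in all groups". A patient who stops after month 6 can therefore already have tissue, baseline risk and two post-surgical risk values.

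The processing-plan section, which is the whole statistical plan, lists descriptive statistics, differences of means, correlation, relative risk and "multivariate logistic regression analysis to evaluate independent associations". It states no analysis population, no missing-data method, no sensitivity analysis and no comparison of eliminated with retained patients. The sample size under Design makes no allowance for loss, and nothing provides for replacing eliminated patients.

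**The concern.** The third specific objective is the association between post-surgical risk modification and the basal metabolic profile. The Justification itself says that benefit is not seen in every patient. Over nine months, willingness to continue may well depend on how much a patient has benefited, and possibly on characteristics that go with the tissue profile. If so, eliminating those who stop selects on something related to the outcome, and the association among those who remain need not be that of the operated cohort.

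Two further things are at stake. The analysed number falls below the planned one with nothing in the plan to compensate. And because insufficiency is undefined, who is eliminated can be settled after the results are known.

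**Working it through.** **1. The plan's own figure.** Under Design, n = z²p(1−p)/d² with z = 1.96, p = 0.20 and d = 0.13:

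1.96² × 0.20 × 0.80 / 0.13² = 0.6147 / 0.0169 = 36.4.

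The protocol shows 0.614 / 0.0169 = 36.3. The figure reproduces and rounds up to 37. It assumes no loss.

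**2. Shrinkage.** The documents give no drop-out rate, so 10–30% is an assumed range. The half-width is 1.96 × √(0.20 × 0.80 / n).

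| Assumed loss | 37 × (1 − loss) | Analysed | 95% half-width |
|---|---|---|---|
| 0% | 37 | 37 | 0.129 |
| 10% | 33.3 | 33 | 0.136 |
| 20% | 29.6 | 30 | 0.143 |
| 30% | 25.9 | 26 | 0.154 |

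The planned 0.13 is missed at each of these loss rates.

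**3. Direction of bias (all values assumed).** Take 50% of patients profile-positive, with benefit in 30% of profile-positive and 10% of profile-negative patients. The cell proportions are 0.15, 0.35, 0.05 and 0.45, so the true odds ratio is (0.15 × 0.45)/(0.35 × 0.05) = 3.86 and the true relative risk is 0.30/0.10 = 3.00. Retain 95% of patients with benefit throughout, and vary retention of those without benefit:

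- 70% in both profile groups: the odds ratio stays 3.86. The relative risk becomes (0.1425/0.3875)/(0.0475/0.3625) = 2.81.
- 60% of profile-positive and 90% of profile-negative: odds ratio 3.86 × 0.90/0.60 = 5.79.
- 90% of profile-positive and 60% of profile-negative: odds ratio 3.86 × 0.60/0.90 = 2.57.

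Uniform 90% retention leaves both measures unchanged. Bias is possible in either direction, and it is not inevitable.

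**4. Size under one specific mechanism (all values assumed).** Take 37 patients, a continuous profile and a continuous benefit at 3, 6 and 9 months. The true slope is 0.50 SD per SD and the residual correlation between visits is 0.6. Drop-out is logistic in the 3-month benefit, with coefficient 1 or 2, calibrated to 10–30% loss and concentrated in patients with little benefit. Simulation gives:

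- 9-month benefit regressed on profile, completers only: slope 0.43 to 0.48, about 3–15% too small.
- Profile regressed on 9-month change, which is the direction the Design section states: slope 0.46 to 0.49. (0.50 − 0.49)/0.50 = 2% and (0.50 − 0.46)/0.50 = 8%.
- A likelihood analysis that also uses the 3-month values: slope 0.50.

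For comparison, the standard error of the slope with all 37 patients is about √(0.75/34) = 0.15, where 0.75 = 1 − 0.50² is the residual variance. A bias of 0.02 to 0.07 is therefore roughly 0.1 to 0.5 standard errors.

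**The case against.** The strongest reply is that the text does not mandate a complete-case analysis. The second criterion has no threshold, so a patient with 3- and 6-month values might be judged sufficient and kept. Part of the rule is also unobjectionable, since without adequate tissue there is no basal profile to analyse. Both points stand. They do not answer the withdrawal criterion, which has no such latitude, or the absence of any method for using partial data. The missing threshold is itself a weakness.

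A reader might infer three stronger things that the documents do not support:

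- **That a complete-case analysis is forced.** It is the practical result of the rule together with a silent analysis section, but it is not prescribed.
- **That elimination necessarily weakens the association.** Step 3 shows that it can be strengthened, weakened or left alone, depending on who leaves.
- **That tissue already taken is thrown away on withdrawal.** Nothing says so. The protocol says that samples are analysed and stored for up to a year before disposal.

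It can also be said that the simulated bias is small, that every input to it is assumed, and that the likelihood analysis recovers 0.50 only because drop-out was made to depend on an observed value. All of that stands, and it limits how much weight the 3–15% can carry. The protocol's direction of analysis is not settled either: Design makes the profile the dependent variable, while the processing plan wants it as a predictor of benefit. That is why both ranges are given.

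**Conclusion.** The point holds as a stated rule whose likely consequence is an analysis of retained patients only. It should be changed, but it is not a fatal flaw.

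The firmest part is the loss of number: 37 falls to 33–26 and the half-width rises to 0.136–0.154 against 0.13, given an assumed 10–30% loss. Bias is conditional. It needs retention to be related to benefit or profile, and its direction cannot be known from the documents. Under drop-out driven by 3-month benefit it is 3–15% of the slope of benefit on profile, or 2–8% in the direction stated under Design. Either is small beside sampling error at this size. The case for changing the rule is that it gives up information already collected and leaves eliminations open to decision after the fact. A large bias has not been shown.

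**What to change.** In the elimination criteria:

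- Make withdrawal end further follow-up only.
- Keep every operated patient with an adequate baseline tissue sample in the analysis.
- Use risk data collected up to withdrawal unless the patient withdraws consent for their use.
- Define insufficient, before the data are seen, as lacking a usable baseline sample or lacking any post-surgical value of the risk variable being analysed. A patient with tissue but no post-surgical value of one variable is left out for that variable only and is still accounted for.

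In the processing-plan section:

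- Add a method that uses all available 3-, 6- and 9-month values under missing-at-random. This can be a repeated-measures mixed model of risk change on basal profile, or multiple imputation before the planned logistic regression. The plan has neither at present. Imputation would keep the existing model.
- Run a completer analysis as sensitivity. It is informative here because the completer odds ratio can survive loss that depends only on the unseen outcome, a case in which missing-at-random fails.
- Report reasons for loss, and the baseline characteristics of lost against retained patients.

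The cost is protocol wording and one added analysis, with no new procedures for patients. The downside is reliance on missing-at-random, which cannot be verified. Enrolling more patients instead, 37/0.9 → 42 to 37/0.7 → 53 for the same assumed losses, would restore the number but not remove any selection.

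### Adipose-tissue morphometry is determined as a degree but typed yes/no in the variable table, with no threshold and no stated analysis form; HOMA is likewise typed only as two classes

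*Combined protocol and SAP*

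**What the plan says.** Four places in the combined protocol and SAP bear on this.

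- **Selection of sources, methods, techniques and procedures for collecting information.** Among the variables listed for analysis in visceral and subcutaneous fat, "the degree of differentiation and hypertrophy of adipocytes and angiogenesis will be determined by morphometric methods of histopathology".
- **Definition of variables and units of measurement.** The same three features share one row, "Differentiation and hypertrophy of adipocytes and angiogenesis". It is labelled dependent and qualitative dichotomous, with the unit "Present or absent". No threshold for presence is given, and the row does not distinguish the three features or the two depots. HOMA is also typed qualitative dichotomous, as "Higher or lower than 15". Serum markers and body fat in the same table are quantitative.
- **Definition of the processing plan and presentation of the information.** The analyses include "difference of averages, correlation, strength of association and relative risk, as well as multivariate logistic regression analysis". From the variables most associated with risk change, "a metabolic profile will be established as a predictive model of the greatest cardiovascular benefit after bariatric surgery". The form in which the morphometric variables or HOMA enter is not stated.
- **Specific objectives and Design.** The third objective is to "Determine the association of the cardiovascular prognosis modification (risk subgroups) with the basal metabolic profile". The Design section says that "the dependent variable is the basal metabolic profile of adipose tissue", and gives convenience of stratifying on risk change as the reason.

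**The concern.** The table is the only place where the plan sets variable types. For the morphometric row, that type is coarser than the measurement described in the data-collection section. If analysts follow the table, a grade or measurement already made on the biopsy is collapsed to two classes before it is compared with the change in cardiovascular risk. This costs power and hides any dose-response pattern in a study of about 37 patients. It touches the main aim, because adipocyte differentiation, hypertrophy and angiogenesis are core parts of the metabolic profile. The predictive model is also built from the variables that show the strongest association, so a marker weakened by a cut may be left out.

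If analysts do not follow the table, the analysis form is undefined and can be chosen after the data are seen. Without a threshold, the yes/no version is undefined as well.

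The role labels add to the uncertainty. With the profile as dependent variable, a binary marker would be the outcome of a logistic model. With the profile as predictive model, markers are predictors and need not be binary.

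**Working it through.** **1. The plan's own figure.** The Design section uses Z = 1.96, p = 0.20 and d = 0.13.

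n = 1.96² × 0.20 × 0.80 / 0.13² = 0.6147 / 0.0169 = 36.4. With the plan's rounded numerator, 0.614 / 0.0169 = 36.3, as stated. Rounded up, this is 37. The figure does not depend on how the markers are typed, so this point leaves it unchanged.

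**2. Information kept by a cut.** Assume a normal marker linearly related to risk change, with share q above the cut. The relative efficiency is φ(z_q)² / [q(1 − q)].

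- q = 0.5: 0.3989² / 0.25 = 0.637, and 0.637 × 37 = 23.6 patients' worth
- q = 0.2: 0.490, or 18.1 patients
- q = 0.1: 0.342, or 12.7 patients

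**3. Power for one marker.** The documents give no distribution, cut share or effect size, so these are assumptions:

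- bivariate normal marker and risk change, with r = 0.3, 0.4 or 0.5
- risk subgroups formed by ranking risk change
- two-sided 0.05, 40,000 simulated studies per setting
- difference-of-averages test, 37 patients split 18 v 19

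| Form of marker | r = 0.3 | r = 0.4 | r = 0.5 |
|---|---|---|---|
| Continuous | 30% | 49% | 71% |
| Three-level grade, equal thirds | 25% | 41% | 62% |
| Binary, cut 50/50 | 21% | 34% | 51% |
| Binary, cut 20/80 | 17% | 27% | 41% |

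Against the even cut, the continuous form gains 9, 15 and 20 points, and the three-level grade gains about 4, 7 and 10 to 11. Repeat runs agree within about 1 point. With no true association, the continuous and evenly cut forms reject in about 5% of runs.

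**4. Sensitivity (continuous v 50/50 cut, difference of averages).**

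- 30 patients, 15 v 15 (assumed eliminations): 24.8/41.0/60.8% v 16.9/27.8/42.0%, a loss of 7.9, 13.2 and 18.8 points.
- 37 patients, 7 v 30 (treating p = 0.20 as the subgroup share, 0.20 × 37 = 7.4): 22.8/37.5/56.3% v 16.9/26.9/39.8%, a loss of 5.9, 10.6 and 16.5 points.
- One-predictor logistic regression, 18 v 19: 32.4/52.2/73.4% v 21.0/34.2/51.0%, a loss of 11.4, 18.0 and 22.4 points. This is slightly overstated, because the null rejection rates are 5.8% and 4.9%.

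These are one-marker tests. They do not represent the full multivariate model.

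**The case against.** **The measured scale may survive.** A reader might infer that the degree is thrown away. The documents do not say so. The data-collection section lists the degree among the variables to be analysed, a degree can be measured first and classified later, and the processing plan names no form. This objection stands, so the loss is conditional on following the table. What remains is that the table types the variable as binary, without a threshold, and nothing overrides it.

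**A degree may be a grade.** The plan does not say whether morphometry yields a continuous measurement or an ordinal score. This also stands. It roughly halves the illustrated gain for a three-level grade, and it means the fix must not impose a continuous type. In the other direction, a 20/80 cut with balanced subgroups loses more than the even cut.

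**HOMA is not a contradiction.** No other section describes how HOMA is obtained or typed, and a threshold class suits relative risk and logistic regression. This is correct. HOMA is a loss-of-information point within the table, resting on the fact that a numeric cut implies a number. Whether 15 is a suitable cut is not judged here.

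**The role order was chosen deliberately.** The Design section gives a reason, and under that order a binary marker could be a logistic outcome. Even so, the processing plan makes the profile a predictor of benefit, so the labels still need aligning. Logistic regression requires a binary outcome but not binary predictors.

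**The study has no power target.** This is true, since the sample size rests on precision of a proportion. The power figures compare forms of the same marker and do not measure a shortfall against a planned level.

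**Conclusion.** The point holds as an avoidable and conditional loss of information, together with an undefined analysis form. The morphometric row is the main case, because two sections describe it differently. HOMA is secondary.

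Under the 18 v 19 set-up with an even cut, the loss in the difference-of-averages test is about 4 to 20 points, depending on whether the recorded scale is a three-level grade or continuous and on the assumed correlation. The upper end holds only for a normal continuous marker. Distribution, cut share, correlation and subgroup split are all assumed.

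A reader might extend the point to every dichotomous row. The documents do not support that. For immunohistochemistry, in vitro tests and insulin sensitivity they describe no underlying scale, and serum markers and body fat are already quantitative. The correction should be made, since it improves the analysis at almost no cost.

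**What to change.** 1. **Variable table.** Reconcile it with the data-collection section. Give differentiation, hypertrophy and angiogenesis a row each, separately for visceral and subcutaneous tissue, typed on the scale on which they are recorded (continuous, or ordinal if graded). Type HOMA as quantitative, on a log scale if skewed.
2. **Processing plan.** State that these forms are primary and used in three ways:
   - a difference of averages, or a rank or trend test if ordinal, between risk subgroups
   - correlation, rank-based if ordinal, with the change in risk measures
   - predictors in the logistic model whose outcome is the cardiovascular-risk subgroup
3. **Binary versions.** Keep them as secondary, with each cut-off stated in advance, including what counts as present.
4. **Roles.** Align the dependent and independent labels in the Design section and the table with the predictive model in the processing plan.
5. **Other tissue and insulin-sensitivity results.** Keep a graded or numeric value only where the assay already yields one.

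The cost is wording in three places and slightly more analysis work. No new samples, readers or procedures are needed.

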Prior signature of informed consent, will include patients with morbid obesity, candidates for bariatric surgery and without additional modifiers of adipose tissue metabolism. Patients will be chosen in accordance with the criteria of the Bariatric Surgery Service, without modifying the routine procedures performed in this service.

At the same time, a group of non-obese patients (obesity comparison group) scheduled and undergoing non-bariatric abdominal surgery (hernioplasty, cholecystectomy, appendectomy, etc.) will be included. In all groups, total body fat, subcutaneous and visceral fat will be determined non-invasively by computed tomography, with the support of the Department of Imaging ([name] and [name]) as described below:

TOMOGRAPHIC MEASUREMENT OF SUBCUTANEOUS AND VISCERAL GREASE

Subcutaneous fat:

The thickness of adipose tissue will be measured, in the abdominal thickest site, at the level of the umbilical scar, with references from the skin to the muscular layer, either in vertical measurement (antero-posterior) or in lateral measurement.

Visceral fat:

Epicardial fat: The thickness of the adipose tissue will be measured epicardial level, in the thickest site.

Preperitoneal fat:

The thickness of adipose tissue will be measured, level of the umbilical scar; from the muscular layer (vertical measurement or ant-post) to the first visceral structure.

Perirenal fat:

The thickness of adipose tissue will be measured perirenal, in the thickest site.

During the surgical act, a sample of 1-2 cubic cm of visceral and subcutaneous adipose tissue will be taken, in all groups, considering all aspects of patient Ethics and Biosafety described in the respective sections of this project. In patients with laboratorial evidence and image of progression to NAFLD, a sample of 1-2 cubic cm of liver tissue will be taken, in accordance with international guidelines for diagnosis and treatment, and with the study protocol established by the service. It will be guaranteed that the taking of biopsies will not affect the course of the surgery. The biological samples acquired will be properly identified, contained and stored for a maximum period of 1 year. Analysis and determinations will be made according to good laboratory practices. Subsequently, they will be treated and disposed of in appropriate bags for disposal. To comply with the provisions of section 6 of NOM-087-ECOL-SSA1-2002 Biological-Infectious Waste.

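### The reference group for normal adipose tissue may include patients operated on for inflamed organs, which could bias its inflammatory markers upward

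*Combined protocol and SAP*

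**What the plan says.** The Design section adds a group of 10 non-obese patients having non-bariatric surgery, for comparing and standardising results. Definition of the control group describes "non-obese subjects subjected to abdominal surgery eg. Hernioplasty, fundoplication etc. to know the" normal metabolic profile of that tissue. The section on selection of sources, methods, techniques and procedures describes what is evidently the same group as "scheduled and undergoing non-bariatric abdominal surgery", and its examples are "hernioplasty, cholecystectomy, appendectomy, etc.) will be included".

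Visceral and subcutaneous fat is sampled during the operation in every group. The listed measurements include tissue markers of inflammation, oxidative stress and endoplasmic reticulum stress, and serum TNFa, CRP and IL-6. The variables table scores tissue pro-inflammatory markers as present or absent.

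There is one set of selection criteria. Its inclusion list contains "With morbid obesity and candidates for bariatric surgery, under the routine of the treating service". Its exclusions are recent medication that could affect fat tissue or cardiovascular risk, "Serious infections in the last month" and "Clinically unstable conditions". No separate criteria are given for the reference group. The processing plan names differences of averages among its methods but has no adjustment or sensitivity analysis by type of reference operation.

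**The concern.** A group meant to show what is normal should not itself carry the process being measured. Cholecystectomy and appendectomy are often performed because the organ is inflamed. That is general clinical knowledge and is not stated in the documents. Inflammation in the abdomen could raise the markers measured in visceral fat and serum at that operation.

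With only ten reference patients, a few such cases would count. Where obesity raises a marker, a raised reference makes the obese patients look closer to normal than they are. Any cut-off or scaling taken from the reference group would carry the same bias. The plan does not say that the surgical indication will be recorded, so the affected patients might not be identifiable afterwards.

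**Working it through.** **1. The two descriptions side by side**

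| | Definition of the control group | Sources, methods and procedures |
|---|---|---|
| Named operations | hernioplasty, fundoplication | hernioplasty, cholecystectomy, appendectomy |
| List closed? | no, examples only | no, examples only |
| Timing | not stated | scheduled |
| Limit on indication | none | none |

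**2. Do the safeguards close the gap?**
- Scheduling describes timing, not indication. It makes acute cases less likely but does not rule out a chronically inflamed gallbladder.
- The infection exclusion is limited to serious infections, so local, chronic or non-infectious inflammation passes.
- A clinically stable patient can still have local inflammation.
- It is unclear whether the exclusions cover the controls, because the inclusion list they accompany requires morbid obesity.
- The obese patients are described as free of other factors that modify fat metabolism. The same is not said of the reference group.

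**3. The plan's own figure**

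The only computed figure is the obese sample size: n = 1.96² × 0.20 × 0.80 / 0.13² = 0.6147 / 0.0169 = 36.37 (36.33 with the rounded 0.614). The plan states 36.3, so it reproduces, and it rounds up to 37. It does not involve the reference group and serves here only as a group size.

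**4. Possible shift of the reference mean**

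The documents give no marker means, SDs or case mix, so k (inflamed controls out of 10) and d (their rise in SD units) are assumptions.

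Shift = (k/10) × d. Spread with f = k/10: √(1 + d²f(1 − f)).

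For k = 2 and d = 2, the shift is 0.4 SD and the spread √(1 + 4 × 0.16) = 1.28. For k = 4 and d = 2, they are 0.8 SD and √(1 + 4 × 0.24) = 1.40.

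**5. What this would do to an obese versus reference comparison**

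*Continuous marker.* Assume a true difference of 1 SD, 37 versus 10 patients, two-sided 5%, and SD held at 1 (the wider spread from step 4 is left out). SE = √(1/37 + 1/10) = 0.356. Power ≈ Φ((1 − kd/10)/0.356 − 1.96).

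*Present/absent marker.* Assume positive rates of 10% in uninflamed controls, 80% in inflamed controls and 60% in obese patients. Expected reference rate = (0.8k + 0.1(10 − k))/10. Power is for Fisher's exact test, by full enumeration.

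| k | Shift, d = 1 | Shift, d = 2 | Power, d = 1 | Power, d = 2 | Reference rate | Fisher power |
|---|---|---|---|---|---|---|
| 0 | 0 | 0 | 80% | 80% | 10% | 84% |
| 1 | 0.1 | 0.2 | 71% | 61% | 17% | 67% |
| 2 | 0.2 | 0.4 | 61% | 39% | 24% | 44% |
| 3 | 0.3 | 0.6 | 50% | 20% | 31% | 24% |
| 4 | 0.4 | 0.8 | 39% | 8% | 38% | 11% |

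The row k = 0 is a real possibility, and then nothing is lost.

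**The case against.** A reader might infer that the two sections contradict each other. They do not. Both lists are examples, and cholecystectomy and appendectomy fit the general description of abdominal surgery in non-obese subjects. What remains is an inconsistency to reconcile.

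A reader might also infer that the exclusions do not apply to the controls. The documents do not settle this. Only one inclusion item mentions morbid obesity, no exclusion item does, and the text goes on to say that patients are included under the selection criteria before it describes both groups. If the exclusions do apply, then together with scheduling they remove many acute cases, though not local or chronic inflammation.

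The strongest counter-argument is about reach. The hypothesis and the objectives relate the baseline profile of obese patients to their own change in cardiovascular risk. None names an obese versus non-obese comparison, and each obese patient is the reference for his or her own postoperative course. Inflammation is also only one part of the profile, beside adipocyte differentiation and hypertrophy, angiogenesis, adipokines and insulin sensitivity. All of this stands and limits the point. It does not remove it, because the plan gives the ten patients the task of showing what is normal and of standardising results.

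Finally, every input to the size is assumed. That is correct, and the figures are illustrations only.

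**Conclusion.** The point holds as a risk of bias. The plan names operations often done for inflamed organs as sources of its normal reference and has no rule that clearly keeps inflamed patients out. Any such patients would push the inflammatory part of the reference upward and understate the difference from the obese group.

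The illustrative shift runs from zero to 0.4 SD at d = 1 and to 0.8 SD at d = 2, with up to four of ten controls inflamed. This rests on the general clinical premise about the two operations and on assumed values of k and d.

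Two stronger readings are not supported. One is that the reference is in fact shifted: the documents do not show that any control will be inflamed. The other is that the obesity difference could be reversed: this needs kd/10 to exceed the true difference, and the documents give no true difference. The consequences are confined to the comparison with the reference group and to anything standardised on it. The within-obese test of the main hypothesis is not directly affected. This is a worthwhile, low-cost improvement.

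**What to change.** - Use one reconciled list in both sections, limited to scheduled operations whose indication is not intra-abdominal inflammation. Copying the hernioplasty and fundoplication list as it stands would not be enough, because it is open-ended and sets no limit on indication.
- Drop appendectomy as a source of controls. Keep cholecystectomy only where the operative and routine histology reports show no inflammation.
- State that the medication, infection and instability exclusions also apply to the reference group.
- Record the surgical indication for each control, and plan a sensitivity analysis that leaves out any control found to be inflamed.

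The cost is a change of eligibility wording, one more data item and somewhat slower recruitment of ten controls. How much slower cannot be estimated, since the plan gives no case mix.
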